# The Effect of a Video-Based Orientation Intervention and Feature Importance Analysis Using Support Vector Regression

### Method

## **Study Design**

This study was designed as a randomized controlled experimental study to evaluate the effect of a video-based orientation training on stress and stigma levels among caregivers of psychiatric patients. Participants were randomly assigned to either the intervention group (receiving video training) or the control group (receiving routine care).

## **Research Questions and Hypotheses**

This study aimed to address the following research questions:

- Is video-based orientation training effective in reducing perceived stress levels among caregivers of psychiatric patients?
- Is the intervention effective in reducing stigmatizing attitudes and beliefs toward psychiatric disorders?
- What are the most important variables that determine perceived stress and stigma levels?

Accordingly, the following hypotheses were tested:

- H1: Video-supported orientation training reduces the perceived stress level of caregivers of psychiatric patients.
- H2: Video-supported orientation training reduces stigmatizing attitudes and beliefs toward psychiatric disorders.
- H3: Perceived stress and stigma levels are influenced by various factors such as the caregiver's demographic characteristics, psychiatric diagnoses, and the caregiving relationship.

## **Place and Time of the Study**

The study will be conducted between July 15 and September 30, 2025, in the closed psychiatric ward of a university hospital located in northeastern Türkiye. The psychiatric unit is a mixed-gender service with a capacity of 16 beds, structured to provide evaluation, treatment, and follow-up for patients with severe psychiatric symptoms. The unit is designed to support both acute intervention and stabilization, ensuring adequate safety and observation. It also organizes educational and social activities to enhance patients' insight, social skills, and adaptation to society. Psychosocial skills training is primarily provided by nurses in collaboration with occupational therapists.

## **Study Population and Sample**

The study population consisted of relatives of patients admitted to the psychiatric unit between July and September 2023 (n=60). Sample size was determined using power analysis with the G\*Power 3.1.9.7 software. Based on the perceived stress scale (PSS) mean scores reported in Zimmerman et al. (2023), the sample was calculated with a 5% type I error, 95% power, and an effect size of 0.924. Statistical analysis indicated that the study should include at least 56 participants (28 in each group). To account for potential data loss, 10% more participants were recruited, resulting in a total of 60 participants (30 in each group). Inclusion criteria: first-degree relatives (parent, spouse, or child) of admitted patients, aged 18 or older, willing to participate, and having sufficient reading, writing, and verbal communication skills. Exclusion criteria included individuals with a psychiatric diagnosis, history of alcohol or substance use, dementia, or other organic mental disorders based on DSM-5.

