#### Randomization

A total of 60 caregivers were randomly assigned to either the intervention or control group (30 each). Group assignment was carried out using the envelope method to prevent bias. Each envelope contained a note stating either "Intervention Group" or "Control Group" and was randomly selected by the participants themselves.

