#### **Perceived Stress Scale (PSS-14)**

Developed by Cohen et al. (1983), this scale assesses perceived stress over the past month. The Turkish adaptation was done by Eskin et al. (2013). It includes 14 items rated on a 5-point Likert scale. Higher scores indicate higher levels of perceived stress. In the current study, Cronbach's alpha was 0.91.

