# Parents' Internalized Stigma of Mental Illness Scale (PISMI)

Developed by Boyd-Ritsher et al. (2003) and adapted to Turkish by Gül-Dikeç et al. (2019), this 29-item scale evaluates internalized stigma in parents of individuals with mental illness. It includes five subscales and uses a 4-point Likert scale. In this study, Cronbach's alpha was 0.96.

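### Ten per cent above the minimum of 56 is 62, not 60; the 60 recruited is 7.1% above and covers two losses per group

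*Protocol*

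**What the plan says.** The sample-size paragraph of the Protocol (Study Population and Sample) goes through three steps.

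- Assumptions: "the sample was calculated with a 5% type I error, 95% power, and an effect size of 0.924". Neither the test nor its sidedness is named.
- Minimum: "at least 56 participants (28 in each group").
- Allowance for losses: "To account for potential data loss, 10% more participants were recruited, resulting in a total of 60 participants (30 in each group").

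The Randomization section repeats the final number: "A total of 60 caregivers were randomly assigned to either the intervention or control group (30 each"). No other loss rate and no rounding rule appears anywhere in the document.

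**The concern.** The allowance sentence tells the reader how many losses the trial can absorb before it falls below its calculated size. As written, it implies that losing one participant in ten is covered. The total of 60 does not deliver that: after such a loss each group would be one person short of the minimum given in the preceding sentence. A base of 56, an addition of 10% and a total of 60 cannot all be right.

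A second, conditional matter sits in the same paragraph. Because the calculation names neither test nor sidedness, the reader cannot tell whether the stated 95% power belongs to the test that will be reported. This is a request for clarification, not a demonstrated error.

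**Working it through.** **Inputs**, all from the Protocol, Study Population and Sample: minimum 56 (28 per group); addition 10%; total 60 (30 per group); type I error 5%; power 95%; effect size 0.924. Reading 0.924 as a standardised mean difference between two independent groups is an assumption.

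**Step 1: can the base of 56 be reproduced?** Power was computed from the noncentral t distribution with 2n − 2 degrees of freedom and noncentrality 0.924 × √(n/2), where n is the size per group. For the Mann-Whitney test n was replaced by n × ARE, with ARE = 3/π for normal data. The smallest n per group reaching 95% power is:

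| Test | One-sided 5% | Two-sided 5% |
|---|---|---|
| t-test | 27 (total 54) | 32 (total 64) |
| Mann-Whitney, normal data | 28 (total 56) | 33 (total 66) |

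The protocol's 28 per group is matched exactly by the one-sided Mann-Whitney test. It does not reach 95% for either two-sided test in the table.

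**Step 2: the allowance.**

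- Ten per cent added to the total: 56 × 1.10 = 61.6, so 62. Per group: 28 × 1.10 = 30.8, so 31.
- Inflation for a 10% loss: 56 / 0.90 = 62.2, so 63, or 64 with equal groups.
- What 60 represents: 60/56 − 1 = 7.1% above the minimum.
- What 60 tolerates: 30 − 28 = 2 losses per group, 4 in total, 4/60 = 6.7%.
- A 10% loss from 60: 60 × 0.90 = 54, or 27 per group, against a minimum of 28.

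Neither convention gives 60. It results only if 30.8 per group is cut down to 30.

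**Step 3: what this does to power** (same method as Step 1, effect 0.924):

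| n per group | One-sided: t / Mann-Whitney | Two-sided: t / Mann-Whitney |
|---|---|---|
| 27 (60 less 10%) | 95.6% / 94.8% | 91.5% / 90.2% |
| 28 (stated minimum) | 96.2% / 95.4% | 92.4% / 91.2% |
| 30 (no losses) | 97.1% / 96.5% | 94.0% / 93.0% |

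The Mann-Whitney columns assume normal data. With logistic data (ARE = π²/9), the two-sided Mann-Whitney test has 94.5% at 28 per group and 95.8% at 30.

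Falling from 28 to 27 per group costs about one percentage point or less. Moving from a one-sided to a two-sided test at 28 per group costs about four.

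**The case against.** The strongest reply is that this hardly matters. The gap is two people, it looks like rounding 30.8 down instead of up, and the minimum of 56 is still exceeded. Even after a 10% loss, one-sided power is 95.6% or 94.8% against a target of 95%. All of that stands, and it is why the point is rated minor. It does not rescue the sentence: rounding down defeats the purpose of a safety margin, and the percentage is still wrong.

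It can also be said that 60 has another origin, since 54/0.90 = 60 exactly and 54 is the one-sided t-test minimum. That is possible, but the document gives 56 as the base, so the text would need correcting either way.

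On power, the reply is that H1 is worded directionally and the Mann-Whitney test is listed under Statistical Analysis, so 56 is consistent with a reading the document supports; test and sidedness may also be settled in an analysis plan that is not shown. This is fair. The two-sided figures are therefore conditional, and there is no shortfall at 28 per group if the test is one-sided.

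Finally, the source population is given as "relatives of patients admitted to the psychiatric unit between July and September 2023 (n=60"). It is a 2023 count, while Place and Time of the Study puts the trial in 2025, so it is weak evidence that 60 is a ceiling. The case for keeping 60 does not need it, because the Randomization section already fixes 60.

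**Conclusion.** The concern holds. Measured against the protocol's own minimum of 56, the total of 60 is an increase of 7.1%, not 10%. It allows two losses per group, and a third loss in either group takes that group below 28. The discrepancy is 2 participants if 10% is simply added, and 3 or 4 if a 10% loss is to be covered. This conclusion is arithmetic on stated figures and needs no assumption.

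Severity is minor, because the consequence for power is small. The power figures rest on reading 0.924 as a standardised mean difference and, for Mann-Whitney, on the assumed shape of the data. On that reading the 95% claim holds for a one-sided test with 28 per group. It would be about 91–92% for a two-sided t-test, or for a two-sided Mann-Whitney test with normal data.

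**What to change.** 1. Keep 60, and replace the statement about 10% by one such as: an allowance of 2 losses per group (4 in total, 6.7% of 60) was added to the minimum of 56.
2. In the sizing sentence, name the test and the sidedness actually used in the power calculation.
3. If H1 is tested two-sided at 5%, restate the power as about 91–92% with 56 evaluable participants (t-test, or Mann-Whitney with normal data).
4. Describe the test as one-sided only if that was fixed before outcome data were seen; otherwise use the two-sided statement. The caution is needed because the document already reports reliability from this study's own data (PSS-14: "alpha was 0.91"; PISMI: "alpha was 0.96"). Those figures show that scale data exist, not that the groups have been compared.

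The cost is wording only: no additional participants and no change to design or analysis. The price is a smaller stated loss allowance and, if the test is two-sided, a lower stated power.

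### The criteria do not limit enrolment to one relative per patient and allocation is by individual, so relatives of one patient can fall in opposite arms and the effect may be diluted

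*Protocol*

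**What the plan says.** The inclusion criteria (Protocol, Study Population and Sample) take in "first-degree relatives (parent, spouse, or child) of admitted patients, aged 18 or older, willing to participate", and the only further requirement is "having sufficient reading, writing, and verbal communication skills". The exclusions concern the relative's own health: "Exclusion criteria included individuals with a psychiatric diagnosis, history of alcohol or substance use, dementia, or other organic mental disorders based on DSM-5". Neither list caps the number of relatives per patient, and neither asks whether the person gives care.

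Elsewhere the participants are called caregivers. H1 reads "Video-supported orientation training reduces the perceived stress level of caregivers of psychiatric patients", Study Design uses the same term, and the Randomization section opens with "A total of 60 caregivers were randomly assigned to either the intervention or control group (30 each".

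Allocation is by person: the envelope "was randomly selected by the participants themselves". The section mentions no family or patient unit. On the setting, the Protocol says "The psychiatric unit is a mixed-gender service with a capacity of 16 beds".

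**The concern.** Applied as written, the criteria let a parent, a spouse and an adult child of the same patient all enrol, and each draws separately. The intervention is largely information and discussion: the unit, stigma, psychiatric disorders, and coping (Procedure). Relatives of one patient can talk about this at home, and the post-test comes one week after the intervention. A control participant whose relative was trained may therefore be partly exposed. That biases the comparison toward no effect, and the analysis cannot reliably undo it afterwards.

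The second gap is smaller. The hypotheses are about caregivers, but the criteria define first-degree relatives. The list should carry the term on which the conclusions depend.

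Both points concern eligibility and the unit of allocation. Those belong in the protocol and are not normally left to a statistical analysis plan.

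**Working it through.** **Inputs from the Protocol.** Effect size d = 0.924, type I error 5% (sidedness not stated), power 95%, stated minimum 28 per group, planned 30 per group (Study Population and Sample); individual 30:30 allocation (Randomization).

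**Inputs that are assumptions.** The Protocol gives no family sizes and no degree of sharing. I take q, the share of participants who enrol as pairs from one family, at 10%, 20% and 40%. I take c, the share of the effect passed to a control relative, at 0.25, 0.5 and 1.

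**Step 1: the plan's own figure.** With the noncentral t distribution, one-sided 5% and 95% power need 27 per arm for a t-test. They need 28 per arm for a Mann-Whitney test with relative efficiency 3/π, which is the stated 56. Two-sided, the requirements are 32 and 33 per arm. The stated size therefore reproduces as a one-sided calculation with independent, uncontaminated participants. Because sidedness is not stated, both versions are shown below. For the t-test at 30 per arm and d = 0.924, power is 94.0% two-sided and 97.1% one-sided.

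**Step 2: chance that a pair is split.** Once one relative is allocated, 30 of the remaining 59 places are in the other arm: 30/59 = 0.508.

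**Step 3: dilution.** The share of controls with a trained relative is f = q × 0.508, and the diluted effect is d′ = 0.924 × (1 − f × c). For q = 0.4 and c = 0.5: f = 0.203 and d′ = 0.924 × (1 − 0.102) = 0.830.

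**Step 4: power at 30 per arm (t-test).**

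| q | c | d′ | Two-sided | One-sided |
|---|---|---|---|---|
| none | – | 0.924 | 94.0% | 97.1% |
| 10% | 0.25 | 0.912 | 93.5% | 96.8% |
| 10% | 0.5 | 0.901 | 92.9% | 96.4% |
| 10% | 1 | 0.877 | 91.6% | 95.7% |
| 20% | 0.25 | 0.901 | 92.9% | 96.4% |
| 20% | 0.5 | 0.877 | 91.6% | 95.7% |
| 20% | 1 | 0.830 | 88.5% | 93.7% |
| 40% | 0.25 | 0.877 | 91.6% | 95.7% |
| 40% | 0.5 | 0.830 | 88.5% | 93.7% |
| 40% | 1 | 0.736 | 80.1% | 88.0% |

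**Step 5: does family correlation itself do harm?** Under individual allocation, the variance of the group difference is multiplied by 1 minus the average pairwise correlation. In the extreme case of 30 pairs with intra-family correlation 0.5, the factor is 1 − (30 × 0.5)/(60 × 59/2) = 1 − 15/1770 = 0.992. Simulation with 10 or 30 pairs and correlation 0.3 or 0.6 gave a type I error of 0.049 to 0.053. Neither figure shows a problem.

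**The case against.** The strongest reply is that the Protocol, read as a whole, enrols caregivers and nowhere says that two relatives of one patient will enter. Both parts are fair. A reader might infer from the criteria that non-caregivers would be recruited, but Study Design, the hypotheses and the Randomization section all say caregivers. The gap is an undefined term in the criteria, and it is not evidence about who would be enrolled.

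A reader might also infer that a 16-bed ward could reach 60 relatives only by taking several per patient. The document does not support this. The window from July 15 to September 30 is 78 days, so 60 patients at one relative each need a mean stay of at most 16 × 78/60 = 20.8 days. If the beds are full on the first day, only 44 new admissions are needed and the limit becomes 16 × 78/44 = 28.4 days. Incomplete consent or occupancy, and time for sessions and post-test, would lower it again. No length of stay is given for comparison, so multiple enrolment is possible but cannot be called likely.

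A third tempting reading is that the listed tests are invalid because relatives are correlated. Step 5 shows that this is not so under individual allocation, and the handling of related observations may in any case be set out in an analysis plan that is not shown.

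Finally, full sharing is an extreme case: one relative's retelling is unlikely to match four facilitated sessions of 45 to 60 minutes. That stands, and it makes the bottom row of the table a bound, not an expectation.

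None of this supplies the missing rule. The criteria still permit split families, and the allocation procedure does nothing to prevent them.

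**Conclusion.** The point holds as a gap in eligibility and in the unit of allocation. It is certain from the text that relatives of one patient may enrol and be allocated separately, and that any such pair is split 51% of the time. How often this would occur, and how much of the effect would pass across, cannot be derived from the document.

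Under the assumed ranges, power at 30 per arm falls from 94.0% to between 93.5% and 80.1% two-sided, or from 97.1% to between 96.8% and 88.0% one-sided. With few pairs and partial sharing (10% or 20% in pairs, at most half passed on), the two-sided loss is at most about 2.4 points (94.0% to 91.6%). The harm is dilution toward zero, not false positives. The change is worth making because it is cheap and removes this route of bias, not because a large loss has been shown.

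**What to change.** Add to the inclusion criteria that one relative per patient is enrolled, the one identified as the main caregiver, and say how that person is identified. This also brings the criteria into line with the hypotheses. With no within-family contamination, the calculated sample size needs no change on this account.

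If a second relative must be admitted, let one envelope decide for the whole family and account for family in the analysis, for example with family-clustered standard errors. If enrolment is already complete, report the number of relatives per patient and any families split between arms.

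The main rule costs one line and a smaller recruitment pool on a 16-bed ward, so recruitment may be slower or 60 harder to reach. The fallback costs precision. The design effect 1 + (m − 1) × ICC, with m the mean number of relatives per family, runs from 1.02 (m = 1.2, ICC 0.1) to 1.50 (m = 2, ICC 0.5). Sixty participants would then be worth between 60/1.02 = 59 and 60/1.50 = 40 independent ones. The values of m and ICC are assumptions. One relative per patient is therefore the better choice where recruitment allows.

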#### Randomization

A total of 60 caregivers were randomly assigned to either the intervention or control group (30 each). Group assignment was carried out using the envelope method to prevent bias. Each envelope contained a note stating either "Intervention Group" or "Control Group" and was randomly selected by the participants themselves.

#### **Data Collection Tools**

Data were collected through face-to-face interviews using a researcher-developed questionnaire, the Perceived Stress Scale-14 (PSS-14), and the Parents' Internalized Stigma of Mental Illness Scale (PISMI).

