#### **Procedure**

This randomized controlled trial was conducted in accordance with the CONSORT guidelines. The PSS-14 and PISMI were administered before (pre-test) and one week after (post-test) the video-based orientation intervention. The intervention included four 45–60-minute video-supported sessions conducted in a suitable meeting room. Training was provided by a psychiatric nurse in collaboration with a psychiatric nursing associate professor. Control group participants received traditional verbal orientation.

Session Content:

- 1. Introduction to the research and psychiatric unit via video and Q&A.
- 2. Explanation and discussion of stigma and personal caregiver experiences.
- 3. Basic knowledge about psychiatric disorders, treatment, and caregiving.
- 4. Understanding and coping with stigma, including influencing factors and family impact.

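### Both outcome scales are taken by face-to-face interview from literate participants who know their arm, an avoidable risk of differential reporting that is clearest for stigma

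*Protocol*

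**What the plan says.** The Data Collection Tools section of the protocol gives the mode of collection: "Data were collected through face-to-face interviews using a researcher-developed questionnaire". The sentence then names the PSS-14 and the PISMI, so the interview covers both outcome scales as well as the background questions. Both are Likert self-report instruments, with 14 and 29 items.

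The other relevant statements are these:

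- **Literacy.** Study Population and Sample makes "having sufficient reading, writing, and verbal communication skills" an inclusion criterion.
- **Knowledge of arm.** Randomization states: "Each envelope contained a note stating either 'Intervention Group' or 'Control Group' and was randomly selected by the participants themselves". Procedure sets four video-supported sessions against a control arm described as: "Control group participants received traditional verbal orientation".
- **Content.** Session 2 in Procedure is "Explanation and discussion of stigma and personal caregiver experiences", and session 4 returns to stigma and how to cope with it.
- **Trainers and timing.** Procedure states: "Training was provided by a psychiatric nurse in collaboration with a psychiatric nursing associate professor". On timing it says: "The PSS-14 and PISMI were administered before (pre-test) and one week after (post-test) the video-based orientation intervention".

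The protocol does not say who conducts the interviews, whether that person knows the allocation, or whether participants can complete either scale in private.

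**The concern.** Perceived stress and internalized stigma are subjective, and answers to such items can shift towards what the respondent thinks is hoped for. Answering an interviewer in person adds to that pressure. The pressure is unlikely to be equal here: one arm has spent four sessions with staff, two of them about stigma, and is asked about its own stigma a week later. The other arm has had routine verbal orientation. Both arms know which group they drew.

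Interviewing both arms in the same way does not cancel a response that differs by arm. The pre-test does not remove it either, because the difference arises after the pre-test. If the shift runs in the expected direction, it would look like the benefit stated in H1 and H2. The protocol specifies no objective outcome that could corroborate a change. The literacy criterion means that the exposure to an interviewer is not needed to obtain the scores.

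**Working it through.** **Reading the sections together**

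1. Mode: interview, for both scales (Data Collection Tools).
2. Participant blinding: none. The note in the envelope names the group (Randomization), and the two arms are visibly different (Procedure).
3. Interviewer blinding or independence: not addressed anywhere.
4. Need for an interview: none stated. Reading and writing are required at entry (Study Population and Sample).
5. Overlap of intervention and outcome: sessions 2 and 4 deal with stigma. No session title names stress. The two outcomes are therefore exposed to different degrees.

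**Illustration of what a reporting shift could do**

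The plan has no figure of its own on this point to reproduce. The only input from the protocol is 30 participants per arm. The shift sizes, the two-sided 5% level and the two-sample t-test are assumptions: the protocol states a 5% type I error without sidedness and lists several possible tests.

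Suppose there is no true effect and reporting differs between arms by b standard deviations. The t statistic then has 2 × 30 − 2 = 58 degrees of freedom and noncentrality b × √(30/2) = 3.873 × b. The two-sided 5% critical value is 2.002. The false-positive rate is the probability that this noncentral t falls outside ±2.002.

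| Assumed shift b (SD) | Noncentrality | False-positive rate |
|---|---|---|
| 0 | 0 | 5.0% |
| 0.1 | 0.387 | 6.7% |
| 0.2 | 0.775 | 11.9% |
| 0.3 | 1.162 | 20.8% |
| 0.4 | 1.549 | about 33% |

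For scale, the effect size used to plan the trial is 0.924. A shift of 0.2 SD is 0.2/0.924 = 22% of that, and it more than doubles the nominal error rate.

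The table describes total differential reporting bias. Participants who fill in a paper form still know their arm and have still attended the sessions, so part of any shift would persist. The documents give no basis for splitting the shift between interview mode and the rest.

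**The case against.** The strongest case on the other side has five parts.

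- **The protocol does not say that items are read aloud, or by whom.** Forms handed out at a meeting and filled in by the participant would also fit the literacy criterion. This cannot be excluded, but oral administration is the natural meaning of an interview. If self-completion was intended, the same one-sentence change settles it. A reader might infer that the trainers did the interviewing. The protocol identifies the trainers but never says that they collect outcomes.
- **The intervention arm was not taught the wanted answers.** This stands in large part. Procedure describes explanation and discussion of stigma, not preferred responses, and no session names stress. A reader might extend the teaching argument to the PSS-14, but the session list does not support that. For stress, only knowledge of allocation and contact with the trainers remain.
- **The direction is not certain.** Talking about personal experiences could make caregivers readier to admit stigma, which would work against H2. This stands as a possibility. Bias in favour of the intervention is the likelier direction, not a proven one.
- **Interviewing is a legitimate choice.** It helps completeness across 14 + 29 = 43 items, and requiring literacy does not contradict it. That is so: the protocol is not inconsistent here. The point is that a less exposed method is available at almost no cost and no reason is given for not using it.
- **It may be too late.** Some sections are in the past tense and report Cronbach's alpha for this study (0.91 and 0.96). Place and Time of the Study, however, speaks of the study in the future. The document does not settle whether data exist, so the fix has to cover both cases.

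**Conclusion.** The concern holds as a design weakness that is cheap to remove. Taking both subjective outcomes by interview, from participants who know their arm and can read and write, without a blinded or independent interviewer, creates an avoidable risk of reporting that differs by arm. The risk probably favours the intervention. It is better founded for stigma than for stress.

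This conclusion rests on reading the interview as oral administration. It is a reasoned risk, not a demonstrated bias, and its size cannot be derived from the document. The range of about 7% to 33% for shifts of 0.1 to 0.4 SD shows only how sensitive a 30-per-arm comparison is to total reporting bias. A reader might take these figures as the effect of the interview, or as what the fix would recover; they are neither.

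**What to change.** Amend Data Collection Tools so that participants complete the PSS-14 and PISMI themselves, on paper and in private, at both pre-test and post-test. Forms should carry a study number only and be returned in a sealed envelope. Keep the interview for the sociodemographic questionnaire.

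The cost is one procedure sentence, with no extra staff and no change in sample size. A few items will be skipped. A check for blanks before sealing, made without reading the answers, reduces this. Some bias from unblinded self-report will remain and should be acknowledged.

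Do not change the mode between one participant's pre-test and post-test, since that would add a mode effect to the change score. If data have already been collected by interview, leave the mode as it was, report it together with who interviewed and whether they knew the allocation, and state it as a limit on the conclusions for H1 and H2.
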